7.3 Data analysis

When possible, generalized linear models (subsuming, for example, logistic regression) will be used to combine data from different dose levels. Model assumptions will be checked graphically prior to analysis. If model assumptions are not met the analysis will be primarily descriptive. Baseline description statistics on all evaluable patients will be provided for demographic variables (age, sex, race/ethnicity), Karnofsky performance status, disease stage and status at the time of enrollment and treatment regimens previously used.

7.4.1 Analysis of the Primary Endpoints

Local control rates for 6 months, 12 months, and 24 months will be analyzed with Kaplan-Meier Survival Curves and the Log-Rank Test.

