2.0 OBJECTIVES

Primary

- 2.1 To determine the efficacy of giving pre-operative radiosurgery to patients pending resection of a brain metastasis. The primary outcome will be measured by local control rate; that is, the tumor volume as measured at a later date and compared to the tumor volume at the start of radiotherapy (time frame: up to 3 years).

Secondary

The secondary objectives of this study are:

- 2.2 To determine the overall survival (OS) as measured by the length of time after the beginning of treatment that diagnosed patient remains alive.
- 2.3 To evaluate distant intracranial failure associated with this therapy as measured by the presence of new brain metastases identified via magnetic resonance image. The imaging will be conducted every 3 months for 12 months, then every 4 months for up to 3 years.
- 2.4 To measure Health Related Quality of Life (HRQL) in patients with primary brain tumors treated with stereotactic radiosurgery using the Functional Assessment of Cancer Therapy-Brain assessment tool for up to 3 years.

The exploratory objective of this study is:

To collect and store the resected body tissue(s) and blood samples for potential correlation to clinical outcome.

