3.6.2 Evaluation during treatment

Administration of stereotactic radio surgery:

Patients will receive a single fraction pre-operative SRS radiation dose. The dose will be determined depending on diameter of the tumor as follows: 24 Gy, 18 Gy, and 15 Gy for tumors < 21 mm, 21-30 mm, and 31-40 mm in maximum diameter respectively.

Dose	Diameter
15 Gy	31-40 mm
18 Gy	21-30 mm
24 Gy	< 21mm

Tumor tissue collection only if participant agrees and there is leftover from clinical collection.

Blood sample collection pre and post SRS treatment (within 24 hours)

Complete physical evaluation with a performance status, vital signs, height, and weight, and a complete medical history

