4.2.2 Justification of sample size/accrual rate

No more than 24 evaluable patients will be treated in the trial. This study of 24 patients will have 80% power to detect a difference in postulated local tumor control of 85% to a known inference local tumor control set at 60% to be excluded, using a 1-sided test with Type I error rate of 0.05 for 6, 12, and 24 months. The sample size was estimated using a non-inferior power analysis for inference of a single proportion compared to a known proportion. Also, an attrition rate of 20% was included into the estimated sample size. Based on previous efforts in recruiting patients at the University of Pittsburgh Cancer Institute, it is anticipated that at least 5 patients per year will be enrolled in the protocol and the accrual will be completed within 5 years. An evaluable patient is defined as one who completes a single fractions of preoperative SRS followed by surgical resection of appropriate brain metastases. Patients who are not evaluable will be replaced.

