7.0 STATISTICAL CONSIDERATIONS

7.1 Study objectives and design

The primary objective of this study is to determine the efficacy of giving pre-operative radiosurgery to patients pending resection of a brain metastasis.

The secondary objectives of this study include:

1. To evaluate overall survival (OS)
2. To evaluate distant intracranial failure associated with this therapy.
3. To evaluate the Health Related Quality of Life (HRQL) associated with this therapy.

This clinical trial is planned as a prospective single-arm phase II study.

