7.2 Sample size and accrual rate

No more than 24 evaluable patients will be treated in the trial. This study of 24 patients will have 80% power to detect a difference in postulated local tumor control of 85% to a known inference local tumor control set at 60% to be excluded, using a 1-sided test with Type I error rate of 0.05 for 6, 12, and 24 months. The sample size was estimated using a non-inferior power analysis for inference of a single proportion compared to a known proportion. Also, an attrition rate of 20% was included into the estimated sample size. Based on previous efforts in recruiting patients at the University of Pittsburgh Cancer Institute, it is anticipated that at least 5 patients per year will be enrolled in the protocol and the accrual will be completed within 5 years. An evaluable patient is defined as one who completes a single fractions of preoperative SRS followed by surgical resection of appropriate brain metastases. Patients who are not evaluable will be replaced.

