7.4.2 Analysis of Secondary Endpoints

1. The patient's overall survival rates for 6 months, 12 months, and 24 months will be analyzed with Kaplan-Meier Survival Curves and the Log-Rank Test.
2. The probability of distant intracranial failure associated with this therapy will be analyzed with Kaplan-Meier Survival Curves and the Log-Rank Test.
3. The analysis of HRQL data will be descriptive. The data will be summarized by question at each time point with the frequency and percentage of each quality level. For each patient, the trajectory of the score will be plotted against time.

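### The trial is sized on a one-sample test of local control against 60%, but section 7.4.1 does not carry that test forward and no deciding time, or any-or-all rule, is given

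*Combined protocol and SAP*

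**What the plan says.** Section 7.1 fixes the design: "This clinical trial is planned as a prospective single-arm phase II study". Section 7.2, repeated in 4.2.2, applies one set of design figures to all three times (6, 12 and 24 months): 24 evaluable patients, 80% power, a postulated local control of 85%, and "a known inference local tumor control set at 60% to be excluded, using a 1-sided test with Type I error rate of 0.05". Section 4.2.2 gives the method: "The sample size was estimated using a non-inferior power analysis for inference of a single proportion compared to a known proportion".

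Section 7.4.1 is one sentence: "Local control rates for 6 months, 12 months, and 24 months will be analyzed with Kaplan-Meier Survival Curves and the Log-Rank Test". Section 7.4.2 uses the same formula for a secondary endpoint: "overall survival rates for 6 months, 12 months, and 24 months will be analyzed with Kaplan-Meier Survival Curves and the Log-Rank Test".

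Section 2.1 describes the primary outcome as tumor volume "as measured at a later date and compared to the tumor volume at the start of radiotherapy (time frame: up to 3 years", without naming a deciding time. The only patient groups in the documents are the three dose and diameter bands in 3.6.2 ("24 Gy, 18 Gy, and 15 Gy for tumors < 21 mm, 21-30 mm, and 31-40 mm in maximum diameter respectively"). Section 7.3 deals with these separately: "generalized linear models (subsuming, for example, logistic regression) will be used to combine data from different dose levels". Neither passage connects the bands to the log-rank test.

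**The concern.** The sample size answers one question: is local control above 60%? The analysis section names a test that, as written, does not ask it. An ordinary log-rank test compares groups, and this trial has one arm. A one-sample log-rank test compares one arm with a reference survival curve, and none is given. Followed literally, 7.4.1 yields curves and no verdict on the hypothesis for which 24 patients were chosen.

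The second gap is the time. The same 60% applies at 6, 12 and 24 months, although local control can only fall with time. Without a stated rule, the analyst can choose after seeing the data which time counts, and whether one success is enough. The handling of patients who die or leave before that time is open in the same way. Eligibility asks for a life expectancy of only 12 weeks (4.4), so this will not be a rare event.

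**Working it through.** **Inputs.** From 7.2: n = 24, p0 = 0.60, p1 = 0.85, one-sided α = 0.05, power 80%, 20% attrition included. From 1.3: cited local control of 97.7%, 84.6% and 64.0% at 6, 12 and 24 months.

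**1. Reproduce the plan's 24.** One-sample proportion, normal approximation:

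n = [(z₀.₉₅√(p0(1−p0)) + z₀.₈₀√(p1(1−p1))) / (p1−p0)]² = [(1.645 × 0.4899 + 0.842 × 0.3571) / 0.25]² = 19.58, so 20.

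With attrition, 20 × 1.2 = 24 (20/0.8 = 25). The plan's figure reproduces as a one-sided, one-sample test against 60%. The same formula with a two-sided 0.05 gives 26 before attrition and 33 after.

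**2. The rule implied by 7.2.** Exact binomial with all 24 assessable:

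- 18 or more: P = 0.096 at 60%, too high.
- 19 or more: P = 0.040 at 60%, and 0.861 at 85%.

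Success therefore needs 19 of 24.

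**3. How much the time matters.** P(X ≥ 19 of 24), if the true rates equalled the cited series:

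| Time | Rate | Chance of success |
|---|---|---|
| 6 months | 0.977 | >0.999 |
| 12 months | 0.846 | 0.85 |
| 24 months | 0.640 | 0.09 |

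**4. A rule that works with censoring.** Lower limit = S^exp(1.645 × se), where se = √Σ[d/(r(r−d))] / |ln S|, d is failures and r is patients at risk. Without censoring:

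- 19/24: S = 0.7917, se = √(5/(24×19)) / 0.2336 = 0.448, limit 0.614. Passes.
- 18/24: S = 0.75, se = √(6/(24×18)) / 0.2877 = 0.410, limit 0.569. Fails.

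This matches step 2. With no failures the formula is undefined; at a true rate of 97.7% that happens with probability 0.977²⁴ = 0.57. The exact limit 0.05^(1/m) then applies, with m patients followed to that time: 0.549 for m = 5 and 0.607 for m = 6.

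**5. Deaths before the chosen time.** Simulation with n = 24, a 12-month landmark, independent exponential failure and death times, scans at 3, 6, 9 and 12 months, and deaths censored at the last scan. The documents give no survival figure for this treatment, so survival is assumed.

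| Alive at 12 months | Type I error | Power at 85% |
|---|---|---|
| 100% | 0.040 | 0.86 |
| 80% | 0.032 | 0.77 |
| 50% | 0.038 | 0.59 |
| 30% | about 0.05 | about 0.45 |
| 16% | about 0.07 | about 0.29 |

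The last row is a low illustration: section 1.1 gives a median survival of 4–5 months with whole brain radiation, a different treatment, and 2^(−12/4.5) = 0.16.

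**6. Scan dates.** Section 3.8 counts scans from surgery, which follows SRS by 1–7 days (3.5, 3.7); objective 2.1 refers to the start of radiotherapy. If the clock starts at SRS and scans fall 4 days late, failures first seen on the 12-month scan are dated after month 12 and count as controlled. Simulated type I error becomes 0.157, 0.127 and 0.108 with 100%, 80% and 50% alive. Hand check with all alive: the rate actually tested is 0.6^(9.13/12) = 0.678, and P(X ≥ 19 of 24) at 0.678 is 0.165, within about 0.01 of the simulation. Assigning each scan to its nominal visit restores 0.039, 0.031 and 0.035.

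**The case against.** **The hypothesis is prespecified.** Section 7.2 fixes the null, alternative, sidedness and α, and a sensible statistician would read the Kaplan-Meier estimate against 60%. This stands in part: a reader might infer that the trial has no hypothesis or is wrongly sized, and step 1 shows otherwise. But 7.4.1 does not state that reading, gives no confidence bound and names no time.

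**A log-rank test can be run on one arm.** True, so it would be too strong to say that no log-rank test could serve. The one-sample form needs a full reference curve, however. A flat 60% at three times does not supply one, and 7.4.1 does not name this version.

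**The log-rank test may be meant across the dose bands.** A reader might infer this and go on to calculate its error rates. No section specifies that comparison, and 7.3 assigns the combining of dose levels to generalized linear models. No weight is placed on it here.

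**The three times may be co-primary.** Section 7.4.1 is headed in the plural, and 7.2 applies the test at all three. If all must pass, no α split is needed. The plan does not say so, and the power would need restating: with complete follow-up, a patient controlled at 24 months was controlled earlier, so the all-three rule reduces to the 24-month test.

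**Three tests at 0.05 might be read as a familywise error of 14.3%** (1 − 0.95³). That assumes independence, and these times are nested. With complete follow-up, an any-of-three rule reduces to the 6-month test. The problem is the undefined claim, not a demonstrated 14% error.

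**Conclusion.** The concern holds. The sized test is not carried into the primary analysis, and neither the deciding time nor an any-or-all rule is given. The operating characteristics in 7.2 belong to a one-sample test against 60% that 7.4.1 does not specify. The open choice is large enough to reverse the conclusion: the chance of success runs from above 0.999 to 0.09 across the three times. Those figures take the cited series as the truth and all 24 patients as assessable; they illustrate sensitivity and do not predict the result.

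This must be fixed before analysis. The power figures with deaths rest on assumed survival and exponential, independent event times. Type I error near 0.03–0.04 rests on scans being assigned to nominal visits and on at least 50% being alive at the chosen time.

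**What to change.** **Section 7.4.1.** Replace the log-rank test as the primary test. Suggested text: *Efficacy is declared if the one-sided 95% lower confidence limit (complementary log-log, Greenwood variance) of the Kaplan-Meier local control rate at [one primary time, named and justified by the sponsor] exceeds 60%. If no local failure is observed by that time, the exact binomial one-sided 95% lower limit, based on patients followed to that time, is used. The other two times are descriptive.* If the sponsor intends three co-primary times, state that all must pass and restate the power.

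**Time zero and scans.** Define time zero once, as SRS or surgery, and reconcile 2.1, 2.2, 3.8, 5.3 and 6.5. Assign each scan to its nominal visit, so that a failure seen on the landmark scan counts at that time.

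**Patients who die or leave.** State how deaths, withdrawals under 6.2 and 8.2, and later whole brain radiation (3.8) enter the analysis. Keep following withdrawn patients for local control where possible, since censoring them may be informative. Report cumulative incidence with death as a competing event alongside.

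**Sections 7.2 and 4.2.2.** Name the same time, state the survival assumed there, and give the resulting power. If survival is expected to be low, choose an earlier time or check the rule by simulation.

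**Section 7.4.2.** Delete the log-rank test and report rates with 95% confidence intervals, or define its groups and label it exploratory.

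**Cost.** Wording only, with no new patients. With a single primary time, the confirmatory claim narrows from three times to one. The restated power may fall below 80% once deaths are allowed for.

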7.4.2 Analysis of Secondary Endpoints

1. The patient's overall survival rates for 6 months, 12 months, and 24 months will be analyzed with Kaplan-Meier Survival Curves and the Log-Rank Test.
2. The probability of distant intracranial failure associated with this therapy will be analyzed with Kaplan-Meier Survival Curves and the Log-Rank Test.
3. The analysis of HRQL data will be descriptive. The data will be summarized by question at each time point with the frequency and percentage of each quality level. For each patient, the trajectory of the score will be plotted against time.

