6.2 Ending subject's participation in the study

A subject's participation in the study will be halted if any one of the following would occur:

- Pregnancy test proves to be positive.
- Disease status becomes worse.
- Develop side effects from treatment.
- Physician feels that this preoperative SRS is no longer in your best interest.
- Patient is not compliant with the study.

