6.5 Post-surgery procedures

Patients will be seen in follow-up 10-14 days post treatment then every 3 months for 12 months, then every 4 months up until 3 years, with the following evaluations:

- Complete physical evaluation with a performance status, vital signs, height, and weight, and a complete medical history
- MRI scans at 3 months post-treatment and every 3 months for 12 months, then every 4 months up until 3 years for assessment of response to therapy and monitoring.
- Administration of Fact-Brain questionnaire at each follow-up visit/scan.

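### Distant intracranial failure is to be estimated by Kaplan-Meier with no rule for deaths, and neither usual handling of deaths gives the probability that Section 7.4.2 names

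*Combined protocol and SAP*

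**What the plan says.** Section 7.4.2, item 2 gives the whole analysis of this secondary endpoint: "The probability of distant intracranial failure associated with this therapy will be analyzed with Kaplan-Meier Survival Curves and the Log-Rank Test". It names no time points, no censoring rule and no groups to compare.

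Section 2.0 (2.3) defines the event "as measured by the presence of new brain metastases identified via magnetic resonance image" and sets the assessment schedule: "The imaging will be conducted every 3 months for 12 months, then every 4 months for up to 3 years". Section 6.5 repeats that schedule, counted from treatment: "MRI scans at 3 months post-treatment and every 3 months for 12 months, then every 4 months up until 3 years". Section 3.8 counts the scans from surgery, which Section 3.5 places 1 to 7 days after SRS. Section 2.0 (2.2) counts overall survival from the start of treatment.

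Death is analysed separately as overall survival (Section 7.4.2, item 1). No section says how a death enters the distant-failure analysis, and none mentions competing events or cumulative incidence.

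On the log-rank test, Section 7.1 says: "This clinical trial is planned as a prospective single-arm phase II study". Size-based dose groups exist (Section 3.6.2: "The dose will be determined depending on diameter of the tumor as follows"), and Section 7.3 says that generalized linear models "will be used to combine data from different dose levels". Item 2 does not say that these groups are to be compared.

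**The concern.** Patients who die without a new brain metastasis can no longer have one detected. Deaths during follow-up are to be expected: Section 4.4 requires a life expectancy of only 12 weeks and a Karnofsky status of at least 50, and follow-up runs to 3 years. A Kaplan-Meier curve for an event that excludes death has to do something with these patients.

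If they are censored, the curve treats them as still able to fail at the rate seen in survivors. With independent deaths, 1-KM then estimates the risk in a setting where nobody dies. If death is made an event, the curve describes failure or death together. Item 2 promises the probability of distant failure, and neither version is that.

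At stake is the accuracy and meaning of one reported secondary result. Under censoring, the published figure can exceed the share of patients in whom distant failure is found, and the gap widens as deaths accumulate.

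**Working it through.** **Plan's own figure.** There is none for this endpoint. The sample size of 24 (Section 7.2) rests on local control of 85% against 60% and is not affected.

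**Step 1: the inequality.** At each failure time t, with d failures among Y at risk, 1-KM (deaths censored) adds KM(t-) × d/Y. The Aalen-Johansen estimate adds S(t-) × d/Y, where S is survival free of both failure and death. S also steps down at deaths without prior failure, so S(t-) ≤ KM(t-), with strict inequality once such a death has occurred. A death after distant failure changes nothing, because that patient has already left the risk set.

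Worked example with 10 patients: deaths at 1, 3, 5, 6 and 8; failures at 2, 4, 7 and 9; one censored at 10.
- 1-KM = 1 − (8/9)(6/7)(3/4)(1/2) = 71.4%.
- Aalen-Johansen = 4/10 = 40.0%, the share who failed.

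In 6,000 random datasets of 3 to 24 patients, 1-KM was never the lower. It was strictly higher in every dataset where a death without prior failure preceded a later failure, and equal in all others.

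**Step 2: illustration of size.** All rates are assumptions, because the documents give no distant-failure rate and no survival planning value for this trial. Net 12-month failure is q = 50%, median survival m is 6, 12 or 18 months, and hazards are constant and independent: λ = −ln(1−q)/12 and μ = ln 2/m. Scans fall exactly at 3, 6, 9 and 12 months (Section 2.0).
- 1-KM(12) = 1 − exp(−12λ)
- Actual incidence = λ/(λ+μ) × [1 − exp(−12(λ+μ))]
- Detected incidence = sum over scans of exp(−(λ+μ)s₀) × exp(−μd) × [1 − exp(−λd)], where s₀ is the previous scan and d = 3 months
- Failure or death = 1 − exp(−12(λ+μ))

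For m = 12 the four scan terms are 0.134 + 0.095 + 0.067 + 0.047 = 0.343.

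| 12 months, q = 50% | m = 6 | m = 12 | m = 18 |
|---|---|---|---|
| 1-KM, deaths censored | 50% | 50% | 50% |
| Actual incidence | 29% | 38% | 41% |
| Detected incidence (Aalen-Johansen target) | 24% | 34% | 39% |
| Failure or death | 88% | 75% | 69% |

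The detected figure is below the actual one because failures arising between the last scan and death are never seen. Over q = 30, 40 and 50%, it is 1 to 5 points low at 12 months.

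**Step 3: scan timing.** Suppose time zero is SRS and scans are timed from surgery 4 days later (within the 1 to 7 days of Section 3.5). The 12-month scan then falls after the landmark, and the last scan counted is at about 9.1 months.

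| 12 months, q = 50%, scans 4 days later | m = 6 | m = 12 | m = 18 |
|---|---|---|---|
| 1-KM | 41.0% | 41.0% | 41.0% |
| Detected incidence | 22.0% | 29.7% | 33.0% |
| 1-KM minus actual (points) | +11.8 | +3.5 | −0.1 |
| Detected minus actual (points) | −7.2 | −7.8 | −8.1 |

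Over the nine combinations of q = 30, 40, 50% and m = 6, 12, 18, the cumulative incidence is the further from actual in six.

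**Step 4: missed scans.** Assume that 20% stop imaging at random by 12 months and that their deaths are still recorded (q = 50%, simulation of 200,000 patients). Aalen-Johansen gives 22, 31 and 35%. Censoring at the last MRI those who die after a missed scan gives 23, 34 and 38%. Actual incidence is 29, 38 and 41%.

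**Step 5: numbers left.** Expected patients alive and failure-free out of 24 are 24 × exp(−(λ+μ)t). With q = 50% this is 3.0, 6.0 and 7.6 at 12 months, and 0.4, 1.5 and 2.4 at 24 months.

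**The case against.** The strongest reply is that Kaplan-Meier is not invalid here. With independent deaths it estimates a legitimate net risk, and it allows comparison with historical rates reported the same way. On that view the only firm fault is that the plan states neither its target nor its rule for deaths, and preferring the cumulative incidence is a matter of taste. The first half stands, and 1-KM can be kept as a labelled companion. The second half does not quite stand: item 2 asks for the probability of failure, and the cumulative incidence is the quantity that answers that, for detected failures.

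A reader might infer that the cumulative incidence is always nearer the true incidence. Step 3 shows that it is not. With late scans the upward shift in 1-KM can offset the loss from undetected failures. That is an accident of timing and no reason to choose 1-KM, but it means accuracy cannot be claimed for the replacement unless the scan window is also fixed. Step 4 adds that, with missed scans, the sensitivity version comes closer to actual than the main one, so both should be reported.

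It is also fair to say that 24 patients give imprecise results. In simulated trials (q = 50%, on-time scans, 12 months) the 95% sampling error was about 24 to 35 points either way for 1-KM and 17 to 19 for Aalen-Johansen. This limits what either figure can show, but the difference between them on the same data is not sampling noise.

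Finally, the missing comparison for the log-rank test is not peculiar to this endpoint. Section 7.4.1 and item 1 of Section 7.4.2 name the test in the same way.

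**Conclusion.** The point holds. Item 2 names a method that, under either usual handling of deaths, does not give the probability it says will be analysed. If deaths without prior distant failure are censored, 1-KM is at or above the cumulative incidence of detected failure from the same data, and strictly above it once such a death precedes a later observed failure. That statement needs no assumed rates.

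The size does. The documents do not fix it. The illustrated gap at 12 months of 11 to 26 points between 1-KM and detected incidence (50% against 39, 34 and 24%) rests on an assumed 50% net failure, median survival of 6 to 18 months, constant independent hazards and on-time scans.

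Three stronger readings are tempting and not supported:
- That the plan overstates distant failure by a known amount. It never says that deaths are censored, it gives no rates, and distance from actual incidence depends on scan timing.
- That every death inflates the estimate. Only a death without prior distant failure that precedes a later observed failure does so.
- That the trial's conclusion is at risk. No threshold or decision in the documents depends on this endpoint, and the sample size concerns local control.

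This should be corrected as a matter of accurate reporting of a named secondary objective.

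**What to change.** In Section 7.4.2, item 2:
- Make the main estimate the Aalen-Johansen cumulative incidence of MRI-detected distant intracranial failure, with death without prior detected distant failure as the competing event.
- Give 95% confidence intervals at 6 and 12 months. Report 24 months descriptively, with the number at risk. Item 2 states no time points; these are taken from item 1.
- State time zero and an analysis window for scans, so that each landmark includes its scheduled scan.
- Censor patients alive without failure at their last MRI. Add a sensitivity analysis that censors at the last MRI those who die after a missed scheduled scan.
- If wanted, show 1-KM beside the main estimate, labelled as a net (no-death) quantity.
- Remove the log-rank test from this item, or name the groups and label the comparison exploratory.

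The cost is a few sentences and standard software. MRI dates are already needed for this endpoint and dates of death for overall survival. Nothing in treatment or follow-up changes.

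There are two downsides. The main figure will not be directly comparable with historical 1-KM rates. It also counts detected failures only: under the assumed rates it is about 1 to 5 points low at 12 months with on-time scans, and about 4 to 8 points low with late or missed scans. The report should say so.
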